5.3.1 Additional On-Treatment Assessments

Tumor Assessments

Tumor assessments will be performed according to RECIST 1.1 and immune related response criteria (irRC) (see Section 11). Response evaluations will be performed week 5 (+/- 1 week) and then every 8 weeks or as clinically indicated. In case of systemic response, confirmatory scans will be performed 4 weeks after the scan that documented response.

Research Blood Sample Collection

CONFIDENTIAL

This document is confidential. Do not disclose or use except as authorized.

Research blood sample collections should be collected at the following time points:

1. At baseline, within 14 days prior to cycle 1 day 1 of protocol therapy (ideally as close to administration of cycle 1 day 1 therapy as possible)
2. At approximately week 4 (following the completion of all radiation therapy) or cycle 2 of pembrolizumab, then again at week 7 or cycle 3, and at then optionally at later pembrolizumab cycles as applicable.

Specific instructions for research blood draw handling are described in Section 9 and appendices.

Tumor biopsy.

If a tumor is readily accessible, a tumor biopsy is suggested at the following time points:

1. At baseline, ideally as close to administration of cycle 1 day 1 therapy as possible
2. After cycle 2, within 14 days prior to cycle 3 day 1 of protocol therapy and generally after restaging scans to be performed on week 5

Further details about collection and handling of tumor biopsy specimen can be found in Section 9 and appendices.

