5.3 On treatment visits

Reasonable effort should be made to conduct study visits on the day scheduled (+/- 3 days).

Patients will also see the treating radiation oncologist as they are receiving radiation as per standard clinical practice.

Any changes from screening clinical evaluation findings that meet the definition of an AE will be recorded on the AE page of the eCRF.

Cycle 1, Day 1

If screening assessments occur within 3 days before start of study treatment, then they may serve as the baseline Cycle 1 Day 1 visit and screening tests do not need to be repeated.

Draw blood sample for:

- Hematology panel (Table 2)
- Chemistry panel (Table 2)

Record:

- ECOG PS
- Weight
- Vital signs
- Physical exam
- Concomitant medication use

CONFIDENTIAL

This document is confidential. Do not disclose or use except as authorized.

Review all laboratory results before administering study treatment.

Criteria to treat at cycle 1 day 1:

- **Absolute neutrophil count $\geq 1000/\mu\text{l}$**
- **Platelets $\geq 75,000/\mu\text{l}$**
- **ALT and AST $\leq 3.0 \times \text{ULN}$ in a patient with no documented liver metastases; ALT and AST $\leq 5.0 \times \text{ULN}$ in a patient with documented liver metastases**
- **Total bilirubin $\leq 1.5 \times \text{ULN}$ ($2.0 \times \text{ULN}$ in a patient with well documented Gilbert's syndrome)**

Every-3-week assessments, day 1 of every cycle:

The following assessments should be performed on the indicated weeks.

Draw blood/collect urine sample for:

- Hematology panel
- Chemistry panel
- TSH (every 3 cycles)

Record:

- ECOG PS
- Weight
- Vital signs
- Physical exam
- Concomitant medication use
- AEs or SAEs

Criteria to treat at day 1:

- **Absolute neutrophil count $\geq 1000/\mu\text{l}$**
- **Platelets $\geq 75,000/\mu\text{l}$**
- **ALT and AST $\leq 3.0 \times \text{ULN}$ in a patient with no documented liver metastases; ALT and AST $\leq 5.0 \times \text{ULN}$ in a patient with documented liver metastases**
- **Total bilirubin $\leq 1.5 \times \text{ULN}$ ($2.0 \times \text{ULN}$ in a patient with well documented Gilbert's syndrome)**

Review all laboratory results before administering study treatment.

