10. STUDY CALENDAR

Baseline evaluations are to be conducted within **28 days** prior to start of protocol therapy (except for pregnancy test and baseline tumor biopsy, as detailed). If these screening assessments occur within 3 days before start of study treatment, then they may serve as the baseline Cycle 1 Day 1 values. Scans must be done within **28 days** prior to the start of therapy. Radiation simulation scan can provide more recent tumor measurements prior to the start of study treatment when available.

As detailed in the Study Calendar, a negative pregnancy test in women of child-bearing potential must be documented within **7 days** before the first dose of study medication.

A baseline tumor biopsy, obtained within **28 days** before starting protocol therapy, is also encouraged if tumor tissue is safely accessible. A second optional tumor biopsy sample will be obtained at the end of cycle 2, within 21 days of cycle 3, day 1.

In the event that the participant's condition is deteriorating, laboratory evaluations should be repeated within 48 hours prior to initiation of the next cycle of therapy.

Assessments must be performed prior to administration of any study agent. Study assessments and agents should be administered within \pm 3 days of the protocol-specified date, unless otherwise noted.

CONFIDENTIAL

This document is confidential. Do not disclose or use except as authorized.

Table 8: Study Calendar

	Screening ^a	C1 D1	C1 D1-D21	C2 D1	C2 D14-D20	Cycle 3 and subsequent cycles	Off-Study ^l	Follow- Up
						D1		
Pembrolizumab ^b		X		X		X		
Radiotherapy ^b			X					
Informed consent	X							
Demographics	X							
Medical history	X							
Concurrent medications ^c	X	X-----X						
Physical exam	X	X		X		X	X	
Vital signs	X	X		X		X	X	
Weight	X	X		X		X	X	
Performance status	X	X		X		X	X	
Hematology panel (CBC with platelets)	X	X		X		X	X	
Chemistry panel ^d	X	X		X		X	X	
Coagulation panel (PT/PTT)	X							
Pregnancy test ^e	X							
EKG	X							
Tumor archival (optional)	X ^f							
Tumor biopsy (suggested)	X ^g				X ^h			
Adverse event evaluation	x	X-----X						
Tumor measurements	X	Tumor measurements are repeated at week 5(+/- week) and then every 8 weeks (+/- week). Documentation (radiologic) must be provided for participants removed from study for progressive disease. Confirmatory scans 4 weeks after documented response will be obtained						X ⁱ
Blood collection for correlative science ^j	X			X		X		
TSH ^k	X					X		

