11.1.4.3 Evaluation of Best Overall Response

The best overall response is the best response recorded from the start of the treatment until disease progression/recurrence (taking as reference for progressive disease the smallest measurements recorded since the treatment started). The participant's best response assignment will depend on the achievement of both measurement and confirmation criteria.

Table 9: For Patients with Measurable Disease (i.e., Target Disease)

Target Lesions	Non-Target Lesions	New Lesions	Overall Response	Best Overall Response for when Confirmation is Required:
CR	CR	No	CR	≥4 wks confirmation
CR	Non-CR/Non-PD	No	PR	
CR	Not evaluated	No	PR	≥4 wks confirmation
PR	Non-CR/Non-PD/Not evaluated	No	PR	
SD	Non-CR/Non-PD/Not evaluated	No	SD	Documented at least once ≥4 wks from baseline
PD	Any	Yes or No	PD	No prior SD, PR or CR
Any	PD*	Yes or No	PD	
Any	Any	Yes	PD	

CONFIDENTIAL

This document is confidential. Do not disclose or use except as authorized.

* In exceptional circumstances, unequivocal progression in non-target lesions may be accepted as disease progression.

Note: Participants with a global deterioration of health status requiring discontinuation of treatment without objective evidence of disease progression at that time should be reported as "*symptomatic deterioration*". Every effort should be made to document the objective progression even after discontinuation of treatment.

Tbale 10: For Participants with Non-Measurable Disease (i.e., Non-Target Disease)

Non-Target Lesions	New Lesions	Overall Response
CR	No	CR
Non-CR/non-PD	No	Non-CR/non-PD*
Not all evaluated	No	not evaluated
Unequivocal PD	Yes or No	PD
Any	Yes	PD

* 'Non-CR/non-PD' is preferred over 'stable disease' for non-target disease since SD is increasingly used as an endpoint for assessment of efficacy in some trials so to assign this category when no lesions can be measured is not advised

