11.2.6 Immune-Related Best Overall Response Using irRC (irBOR)

irBOR is the best confirmed overall response over the study as a whole, recorded between the date of first dose until the last tumor assessment before subsequent therapy (except for local palliative radiotherapy for painful bone lesions) for the individual subject in the study. For the assessment of irBOR, all available assessments per subject are considered.

irCR or irPR determinations included in the irBOR assessment must be confirmed by a second (confirmatory) evaluation meeting the criteria for response and performed no less than 4 weeks after the criteria for response are first met.

11.2.7 Local response is defined as irRC applied to the irradiated lesions. This is not applicable in the case of an irradiated bone lesion.

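### The confirmatory scan is scheduled at exactly 4 weeks with no window of its own, so a scan done on schedule at 25 to 27 days cannot meet the 4-week minimum for confirming a response.

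*Combined protocol and SAP*

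**What the plan says.** Two places schedule the confirmatory scan. Section 5.3.1 says: "In case of systemic response, confirmatory scans will be performed 4 weeks after the scan that documented response". The tumor-measurement row of Table 8 in section 10 says: "Confirmatory scans 4 weeks after documented response will be obtained". Neither attaches a window to this scan.

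The tolerances in the document are these:

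- Section 10, general rule: "Study assessments and agents should be administered within \pm 3 days of the protocol-specified date, unless otherwise noted".
- Section 5.3, on-treatment visits: "Reasonable effort should be made to conduct study visits on the day scheduled (+/- 3 days" in either direction.
- Table 8, routine scans: "Tumor measurements are repeated at week 5(+/- week) and then every 8 weeks (+/- week" in either direction. This wording covers the week 5 and 8-weekly scans. The confirmatory scan is named later in the same row without a tolerance.

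Two places say what counts as confirmation. Table 9 in section 11.1.4.3 gives "≥4 wks confirmation" for complete and partial response, and the text above it says that a participant's "best response assignment will depend on the achievement of both measurement and confirmation criteria". Section 11.2.6 requires the second evaluation for irCR or irPR to be "performed no less than 4 weeks after the criteria for response are first met".

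**The concern.** The schedule gives a point target equal to the minimum that the response criteria require. Any tolerance with an early side therefore allows scans that follow the schedule but fail the criteria. A coordinator booking from Table 8 has no signal that an early scan is worth less than a late one.

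A responder scanned on day 25, 26 or 27 stays unconfirmed until another qualifying scan. On treatment, the next routine scan is nominally 8 weeks after the responding scan. If the response ends first, or the patient dies or starts new therapy, the patient could be recorded in a lower best-response category only because the scan came one to three days early. The error can run in one direction only, towards fewer confirmed responses. Overall response by RECIST 1.1 and by irRC is a named secondary endpoint (sections 1.3 and 13.5). Section 13.1 describes a population that tends to progress within a few months, so loss of response between week 4 and week 8 is plausible.

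**Working it through.** The plan states no figure on this point. The check is a day count, followed by an illustration of size.

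**Inputs.** Target: 4 weeks = 28 days (5.3.1, Table 8). General tolerance: plus or minus 3 days (section 10). Minimum interval for confirmation: at least 28 days (Table 9, 11.2.6). Routine interval: 8 weeks = 56 days (5.3.1). Off-treatment interval without progression: 6 weeks = 42 days (5.3.2, 5.3.3). Patients in a cohort that completes both stages: 19 (13.1). Intervals: 90% exact binomial (13.5).

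**Day count under the general tolerance.**
- Allowed days: 28 − 3 = 25 to 28 + 3 = 31, which is 7 days.
- Days below 28: 25, 26 and 27, so 3 of 7 (3/7 = 43%).

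**Day count if the routine-scan tolerance of plus or minus 1 week is borrowed instead.**
- Allowed days: 28 − 7 = 21 to 28 + 7 = 35, which is 15 days.
- Days below 28: 21 to 27, so 7 of 15. This reading widens the conflict.

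**Time to the next chance to confirm.** The next routine scan falls nominally 56 days after the responding scan. That is 56 − 27 = 29 to 56 − 25 = 31 days after the early scan, unless a scan is done sooner on clinical grounds.

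**Size of one lost response.**
- 1/19 = 5.3 percentage points.
- Example: 3/19 = 15.8% (90% CI 4.4% to 35.9%) becomes 2/19 = 10.5% (90% CI 1.9% to 29.6%).

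**How often, on assumed inputs only.** The share of responders lost is (share of confirmatory scans that are early) × (share of those responses gone before a later qualifying scan). Neither factor is in the documents. Taking 1/7 to 3/7 for the first and 10% to 50% for the second:
- Low end: 1/7 × 0.10 = 0.014, about 1%.
- High end: 3/7 × 0.50 = 0.214, about 21%.

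The width of this range shows that the documents do not settle the frequency.

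**After the fix.** With a window of 0 to +7 days, the allowed days are 28 to 35, and 0 of 8 fall short.

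**The case against.** The strongest reply is that the stated rules agree: a scan on day 28 satisfies both the schedule and the criteria. The conflict appears only when a general tolerance is brought in, and that tolerance yields where something else is noted. Section 5.3.1 refers tumor assessments to section 11, so the section 11 minimum could be read as the exception. The section 5.3 tolerance concerns visits and does not mention scans. This reading is possible, but neither scheduling place states it. A site working from Table 8 would have to infer it.

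Three further objections stand and limit the point.

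- An early scan does not forfeit the response. Section 11.2.6 considers all available assessments up to subsequent therapy, and 5.3.1 allows scans when clinically indicated, so a later scan can confirm.
- A reader might infer that stopping treatment loses the response. The documents do not support that: sections 5.3.2 and 5.3.3 continue tumor assessments every 6 weeks for patients who stop without progression.
- Section 13.5 does not say that the reported response rates are confirmed rates, and the relevant column of Table 9 is headed conditionally, for when confirmation is required. The link to the reported rates comes from section 11.

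A reader might also take 3 of 7 as the share of confirmatory scans that will fail, or even of responses that will be lost. It is neither. The first use needs scan days spread evenly over the window, which nothing in the documents supports. The second also ignores later confirmation.

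**Conclusion.** The mismatch is real and minor. Under the general tolerance, days 25 to 27 are on schedule and cannot confirm a response. The conclusion rests on applying that tolerance to a scan with no window of its own; borrowing the routine-scan tolerance makes the conflict larger.

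The supportable consequence is that a response could be lost from the confirmed RECIST 1.1 or irRC best overall response, and that those secondary rates could be biased downward. A firm statement that they are biased would go too far. Loss needs an early scan, no qualifying repeat, and an end to the response, death or new therapy before the next scan. Each lost response would cost 5.3 points in 19 patients. The 3-in-7 figure is illustrative only.

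The primary endpoint and both stages of the decision rule use progression-free status at 3 months and are untouched. Abscopal response (11.2.8) carries no confirmation requirement. Local response (11.2.7) could be touched only because it is defined through irRC.

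**What to change.** In section 5.3.1 and in Table 8, schedule the confirmatory scan at least 4 weeks (28 days) after the scan that first showed response. Give it a window with no early side, for example 0 to +7 days, and state that the general tolerance of plus or minus 3 days does not apply to it. The +7 is a suggestion; what matters is that no allowed day falls before day 28. While the text is open, section 13.5 could also say whether the reported response rates are confirmed.

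The cost is a sentence in each place. No scan is added. The price is that confirmation may come a few days later.

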5.3.2 End-of-Treatment Procedures

End-of-Treatment Visit

All subjects will be asked to return to the site for a final, End-of-Treatment visit, if possible. This visit must be performed within 30 days of final administration of study treatment. End-of-treatment assessments will not have to be repeated if the same assessments were performed within 7 days of this visit.

Record:

- For patients who come off for reasons other than progressive disease: Tumor assessments to be performed every 6 weeks if patients come off within one year of therapy. If study treatment is discontinued due to PD, then tumor assessments are not required for that subject.
- ECOG PS
- Physical exam
- Vital signs and weight
- Concomitant medication use
- AEs or SAEs

Draw blood sample for:

- Hematology (Table 2)
- Chemistry panel (Table 2)

5.3.3 Follow-up Period Procedures

Subjects who do not have PD upon discontinuation of study treatment are required to have tumor assessments during the post-treatment follow-up period (using the same methodology and acquisition techniques as were used for previous assessments). Response evaluations will be

CONFIDENTIAL

This document is confidential. Do not disclose or use except as authorized.

performed every 6 weeks. Further details about collection and handling specimens can be found in Section 9 and appendices.

5.4 Agent Administration

5.4.1 Pembrolizumab

Pembrolizumab administration

Sponsor Merck will provide each investigator with adequate supplies of pembrolizumab. Pembrolizumab will be administered by trained medical personnel at the investigational site. Treatment compliance will be monitored through documentation of study treatment administration in the subject's medical record.

Pembrolizumab will be administered in clinic every 21 days (+/- 5 days) during each cycle. It will be administered as a 30 minute IV infusion. Given the variability of infusion pumps from site to site, a window of -10 and +45 minutes is permitted (i.e., infusion time is 30 minutes: -10 min/+45 min).

The Investigator's Brochure contains specific instructions for the preparation of the pembrolizumab infusion fluid and administration of infusion solution.

5.4.2 Radiation treatment

5.4.2.1 Prioritizing lesions for irradiation

In addition to providing palliative benefit, this study attempts to use radiation to engender a systemic immune response in the context of PD-1 inhibition. Therefore, the choice of site or sites irradiated will be based on a combination of safety, palliative benefit and, if feasible, correlative studies will in parallel evaluate whether there is an association between abscopal responses and personalized stratification based on hypothetical T-cell trafficking[61]. Prior to radiation simulation, initial staging scans will be analyzed in detail. Lesions will be prioritized for treatment as follows (in order of priority): 1) Lesions must be safe to irradiate at the dose prescribed by the protocol as deemed by the treating radiation oncologist and able to meet standardly accepted radiation dose constraints and as specified below; 2) Lesions must be irradiated for potential palliative benefit as determined by the treating physicians; 3) Lesions that have not responded or progressed on prior immune checkpoint blockade. 4) The largest lesion that meets the criteria states above determined using bidirectional measurements. Based on this algorithm, the top rated lesion will receive 8 Gy in each of 3-5 fractions. In cohort B, the goal is to irradiate a significant percentage, if not all of the total visible tumor burden.

In parallel, we will investigate the feasibility of ranking all metastatic lesions in terms of the theoretic potential of these lesions to stimulate an immune response at a distant, unirradiated metastatic site as described in more detail in the correlative studies section.

5.4.2.2 Treatment simulation: The treatment planning process will include CT based simulation with 1.25- 2.5-mm cuts to cover the area(s) of interest.

CONFIDENTIAL

This document is confidential. Do not disclose or use except as authorized.

5.4.2.3 Contours: Several tumor contours will be defined by the physician:

CTV1-4 (CTV): Tumor volumes to be treated. CTV1-3 will be treated to 5-8 Gy in each of 3-5 fractions. In cohort B, CTV2-6 will be treated to 20 Gy in 5 fractions. These volumes include gross disease; elective irradiation to other areas is generally not permitted. An optional 0-2 cm margin on gross disease (GTV) is allowed when determining the CTVs at the treating radiation oncologist's discretion to account for any uncertainty or microscopic disease. For targets that have significant motion (e.g. lung or liver targets), 4D-CT planning with delineation of an internal target volume (ITV) is recommended, and other motion management (e.g. gating/compression systems) may be used. The exact margins are patient- specific. A 2mm – 1cm planning tumor volume (PTV) margin added to the CTV will also be included to account for set up variation, (and internal target motion), as appropriate to each individual lesion.

5.4.2.4 Several contours of the organs at risk will be defined by the physician and/or treatment planner if visible within the axial slices covered by CTV1.

- Spinal cord
- Brainstem
- Brachial plexus
- Cauda equina
- Cochlea
- Esophagus
- Heart/pericardium
- Trachea and ipsilateral bronchus
- Skin
- Stomach
- Duodenum
- Jejunum/ileum
- Liver
- Kidneys
- Lung
- Optic structures (Globes, right and left optic nerves and optic chiasm)

5.4.2.5 Prescriptions:

Target1-3 (CTV1-3+ individualized PTV margin) will be treated to a dose of 8 Gy in each of 3-5 fractions.

Target2-6 (CTV2-6 + individualized PTV margin) will be treated to a dose of 20 Gy in 5 fractions for patients in cohort B.

Photons or electron treatments are allowed, but graphic plans are mandated. Planning may be electron based, 3D conformal, IMRT or SBRT, as appropriate to each individual case / lesion to achieve coverage of the PTV target and maintain normal tissue tolerance. The percentage PTV covered to 100% of the prescription dose will be reported; reasonable effort should be made to

CONFIDENTIAL

This document is confidential. Do not disclose or use except as authorized.

keep this greater than 95% while maintaining normal tissue dose constraints as indicated below. Bolus may be used as appropriate.

5.4.2.6 Timing of radiation treatment

- Cohort A: Three to five treatments of 8 Gy will be delivered no more frequently than every other day and over a period that does not extend over more than 21 days. Pembrolizumab will be given within 10 days after starting radiotherapy treatment, or up to 3 days prior to radiotherapy start.
- Cohort B: Three treatments of 8 Gy will be delivered no more frequently than every other day and over a period that does not extend over more than 21 days. Pembrolizumab will be given within 10 days after starting radiotherapy treatment, or up to 3 days prior to radiotherapy start. 20 Gy in 5 fractions will be delivered to an additional 1-3 lesions that do not require urgent palliation.

5.4.2.7 Organs at risk (OAR) – Treating radiation oncologists will abide by accepted radiation dose constraints, especially in regards to 8 Gy fraction treatment. For patients in Cohort B, a cumulative dose calculation is recommended when irradiated lesions are in close proximity. Guidance for dose constraints are provided in the table 3 below.

Table 3:

Constraints for 3 fraction treatment

Structure	Volume (mL)	Volume Max (Gy)	Max Point Dose (Gy)
Spinal cord	<0.25	18	19.5
Brainstem	<1	18	23
Brachial plexus	<3	22.5	24
Cauda equina	<5	21.9	24
Cochlea			20
Esophagus	<5	21	27
Heart/pericardium	<15	24	30
Trachea and ipsilateral bronchus	<4	15	30
Skin	<10	22.5	24
Stomach	<10	21	24
Duodenum	<5	15	24
Jejunum/ileum	<5	16.2	27

CONFIDENTIAL

This document is confidential. Do not disclose or use except as authorized.

Liver	700mL spared from volume max	17.1	
Kidneys	200mL spared from volume max	14.4	
Lung	1000mL spared from volume max	11.4	
Optic structures	<0.2	15	19.5

Constraints for 5 fraction treatment

Structure	Volume (mL)	Volume Max (Gy)	Max Point Dose (Gy)
Spinal cord	<0.25	22.5	D0.035<30
Brainstem	<0.5	23	30
Brachial plexus	<3	27.5	D0.035<35
Cauda equina	<5	30	35
Cochlea			25
Esophagus	<5	20	35
Heart/pericardium	<15	32	38
Trachea	<4	18	35
Skin	<10	30	D0.035<32
Stomach	<10	18	32
Duodenum	<5	18	32
Jejunum/ileum	<5	20	32
Liver	700mL spared from volume max	21	
Kidneys	200mL spared	17.5	

CONFIDENTIAL

This document is confidential. Do not disclose or use except as authorized.

	from volume max		
Lung	1500mL spared from volume max	13	
Optic structures	<0.2	22	25

Note: If there is any overlap with prior radiation treatment fields, max point dose administered to the brainstem and spinal cord and optic structures in the area of prior overlap should be limited to 12 Gy.

PTV coverage may be compromised to ensure an acceptable plan.

